19.3 Angioedema Quality of Life Questionnaire – American English Version 2012

Instructions for evaluation of the AE-QoL

The structure of AE-QoL

AE-QoL consists of four dimensions and a total score

Functioning

- 1. Impairment of work
- 2. Impairment of physical activity
- 3. Impairment of spare time activities
- 4. Impairment of social relations

Fatigue/Mood

- 6. Difficulties of falling asleep
- 7. Waking up during the night
- 8. Feeling tired during the day
- 9. Difficulties in concentrating

Shire SHP616-300 Statistical Analysis Plan idursulfase IT

17 Aug 2017

10. Feeling downhearted

Fears/Shame

- 12. Feeling burdened at having swellings
- 13. Fear of new suddenly appearing swellings
- 14. Fear of increased frequency of swellings
- 15. Ashamed to visit public places
- 16. Embarrassed by the apppearence of swellings
- 17. Fear of long term negative drug effects

Nutrition

5. General limitations in foods and eating

11. Limitations in the selection of food and beverages

Total Score

Items 1 to 17

How to calculate AE-QoL scales and the AE-QoL total score

AE-QoL is meant to be evaluated by using its four individual dimensions (profile instrument) but is can also be used to determine a total score (index instrument):

The AE-QoL dimension scores as well as the AE-QoL total score are calculated by using the following formula:

(Σ items – min Σ items / max Σ items – min Σ items) x 100 *Example:* Dimension "Functioning": Item 1: answer 3 Item 2: answer 2 Item 3: answer 4 Item 4: answer 5 Σ items: (3+2+4+5) = 14min Σ items: (1+1+1+1) = 4max Σ items: (5+5+5+5) = 20Enter values in formula: $(14 - 4/20 - 4) \times 100 = 62.5\%$

The AE-QoL dimension scores correspond to the mean of the items within each dimension. If some items are missing, the total of the items within the dimension is divided by the number of the non missing items.

The same holds for the AE-QoL total score.

An AE-QoL dimension score should not be calculated if more than one item is missing in that dimension.

The AE-QoL total score should not be calculated if more than 25% of items (>4 items) are missing.

Please note that only calculating the raw dimension scores (mean of the item scores within each scale) and the raw total score score (mean of all item scores) would be easier than the above described procedure. However, in case of missing answers, an interindividual as well as an intraindividual comparison of AE-QoL results would be limited. The above described linear transformation of all raw scores into percentage scores (indicating the location of the raw scores in relation (in percent) to its maximum possible score) solves this problem and makes it possible to judge and compare AE-QoL results even when single items are missing. The linear transformation of raw scores results in minimal and highest possible scale and total scores of 0 and 100, respectively.

19.4 Major Protocol Deviations

The following protocol deviations are classified as major protocol deviations that may affect the primary efficacy endpoint. Subjects who satisfy these protocol deviations will be excluded from the Per-protocol Set.

- 1. Subject <12 years and subject was randomized into the study (I1)
- 2. Subject was NOT diagnosed by a physician to have HAE (Type I or II) and subject was randomized into the study (I2)
- 3. Subject was NOT diagnosed by a physician to have a functional C1 inhibitor (C1 INH) level less than 50% of normal and subject was randomized into the study (I2)
- Adult subject currently receiving prophylactic therapy with C1 INH, NOT having a history of ≥2.0 angioedema attacks per month (average) during the 3 consecutive months prior to starting prevention therapy and subject was randomized into the study (I3)
- Subject (>12 years of age) not receiving prophylactic therapy with C1 INH, NOT having a history of ≥2.0 angioedema attacks per month (average) during the 3 consecutive months prior to the screening visit and subject was randomized into the study (I3)
- Adult subject currently receiving a stable dose of attenuated androgens, NOT having a history of ≥2.0 angioedema attacks per month (average) during the 3 consecutive months prior to the screening visit and subject was randomized into the study (I3).
- 7. Adults (>18 years of age) receiving prophylactic IV CINRYZE that exceeds the approved dosing regimen of 1000 U every 3 or 4 days (receiving a weekly dose >2000 U). (E1)
- Adolescents (>12 and <18 years of age) currently receiving prophylactic therapy with C1 INH. (E2)

CONFIDENTIAL

- 17 Aug 2017
- 9. Have received any C1 INH therapy or any blood product for the treatment or prevention of angioedema attacks within 3 calendar days prior to the first dose of investigational product in Treatment Period 1. (E4)
- 10. If female, have started or changed the dose of any hormonal contraceptive regimen or hormone replacement therapy (ie, estrogen/progestin containing products) within 2 months prior to the screening visit. (E5)
- 11. Have a history of hypercoagulability (abnormal blood clotting) or other predisposition for thromboembolism. (E6)
- 12. Have a diagnosis of acquired angioedema or known presence of anti-C1 INH antibodies. (E7)
- 13. Have a history of allergic reaction to C1 INH products, including CINRYZE (or any components of CINRYZE), or other blood products. (E8)
- 14. Be pregnant or breastfeeding. (E9)
- 15. Have received an investigational drug within 30 days prior to the first dose of investigational product in Treatment Period 1. (E10)
- 16. Have, as determined by the investigator and/or the sponsor's medical monitor, any surgical or medical condition that could interfere with the administration of investigational product or interpretation of study results. (E11)
- 17. Subject administered "damaged" IP (e.g., IP with unapproved temperature excursion)
- 18. Calculated study drug compliance of <85% among subjects whose treatment duration is at least 6 weeks in the treatment period.
- 19. Subject missed \geq 3 consecutive doses
- 20. Subject was randomized but did not receive study drug
- 21. Investigator did not complete a separate angioedema attack CRF for each attack based upon their review of the data in the subject eDiary.
- 22. Concomitant use of Use of C1 INH therapy (other study drug) for prophylaxis against angioedema attacks after randomization upto 1 wk FU period
- 23. Initiation of long term therapy (including IV C1-INH, Transexamic acid or androgen therapy) after randomization upto the last dose
- 24. Change in dose of hormonal contraceptive regimen or hormone replacement therapy (ie, estrogen/progestin containing products) after randomization

- 25. Study drug is restarted later than 30 days of the temporary interruption after a Thrombotic/Thrombo-embolic event
- 26. Accidental Unblinding
- 27. Subject receiving 3 or more consecutive doses of incorrect treatment assigned by IXRS
- 28. Study drug exposed to temperature excursion (deemed unusable by Shire) dispensed to subject with reported AEs being associated with the exposed drug in the opinion of the PI.

HRQoL STATISTICAL ANALYSIS PLAN

Protocol No.:	SHP616-300
Project No.:	0238-0431
Protocol Title:	A Phase 3, Randomized, Double-blind, Placebo- controlled, Two-period, Three-sequence, Partial Crossover Study to Evaluate the Efficacy and Safety of Subcutaneous Administration of 2000 IU of C1 Esterase Inhibitor [Human] Liquid for Injection for the Prevention of Angioedema Attacks in Adolescents and Adults with Hereditary Angioedema: Assessment of Health-related Quality of Life (HRQoL)
Drug:	SHP616, C1 esterase inhibitor [human] liquid for injection
Sponsor:	Shire Development LLC and International Affiliates [name]
Version No. and Date:	Version 0.6, Date 22 August 2017

Version No:	Document History Description of Update	Author(s)	Effective Date

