7.2.2.2 Recording of Angioedema Attacks in the Electronic Subject Diary

During the study, subjects will use an electronic subject diary each day to record any symptoms or occurrences of an angioedema attack. The investigator will complete a separate angioedema attack CRF for each attack based upon their review of the data in the subject diary. Information will include the following:

- Date and time of onset and complete resolution of angioedema attack symptoms
- Characterization of whether swelling or pain is (indicate all that apply):
 - Mucosal (pharyngeal, laryngeal, gastrointestinal, genitourinary)
 - Non-mucosal (truncal, extremity, facial)
- Location (site) of the swelling or pain (indicate all that apply):
 - Upper airway (includes laryngeal or pharyngeal)
Note: Pharyngeal or oral swelling that results in airway compromise will be classified as a laryngeal attack.
 - Gastrointestinal/abdominal (including symptoms of pain, nausea, vomiting, swelling, and/or change in bowel habits)
 - Genitourinary (including scrotum or vulva)
 - Cutaneous (facial)
 - Cutaneous (extremity, peripheral, or torso [eg, buttocks, external head/neck, trunk])
- Severity (intensity) of the sign/symptom at each location listed:
 - Absent
 - Mild: the angioedema attack sign/symptom(s) is noticeable but is easily tolerated by the subject and does not interfere with routine activities.
 - Moderate: the angioedema attack sign/symptom(s) interferes with the subject's ability to attend work/school or participate in family life and social/recreational activities.

- Severe: the angioedema attack sign/symptom(s) significantly limits the subject's ability to attend work/school or participate in family life and social/recreational activities.
- Visual Analogue Scale (VAS) pain measurement score
- Angioedema attack trigger(s)
- Answer to the question, "Was treatment administered for the attack?" If yes, record the date, time, and name of treatment administered.

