4.6 Per-protocol Set

All subjects in the Full Analysis Set who complete scheduled primary assessments for 6 study weeks and who do not have pre-defined protocol deviations that may affect the primary efficacy endpoint will be included in the Per-protocol Set. Refer to Appendix 19.4 for the protocol deviations that exclude subjects from the Per-protocol Set.

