10. EFFICACY ANALYSES

10.1 Primary Efficacy Variable(s) and Analysis

The primary efficacy analysis will be conducted over the subjects in the Full Analysis Set that are randomized to Treatment Sequence 1 (A/B) or 2 (B/A) to evaluate of the efficacy of SC administration of C1 esterase inhibitor [human] liquid for injection compared to placebo.

The primary efficacy endpoint is defined as the normalized number of angioedema attacks during a treatment period. The NNA is expressed as the number of attacks per month (ie, 30.4 days) of exposure:

NNA = 30.4 x (number of attacks during treatment period)/(days of treatment period)

If a subject discontinues during the treatment period, the denominator of the NNA will be the days on treatment for that subject; this is equivalent to the last observation carried forward imputation method to impute the missing information following the subject's discontinuation.

To test the hypothesis that the NNA of C1 esterase inhibitor [human] liquid for injection is greater than or equal to the NNA of placebo, and the alternative hypothesis that the NNA of C1 esterase inhibitor [human] liquid for injection is less than the NNA of placebo as below:

H_{0:} μ _{C1 INH} - μ placebo ≥ 0 VS H_{1:} μ _{C1 INH} - μ placebo < 0

A linear mixed effect model will be performed to analyze the primary efficacy endpoint with period, sequence, use of prophylactic therapy with C1 INH, which is derived by long-term prevention with C1 INH at randomization, and treatment as fixed effects, and subject nested within sequence as a random effect. If the variance-covariance matrix of random effects is not positive definite, a mixed effect model with the same fixed effects and subject nested within sequence as repeated measurements will be performed instead; the repeated measurement is equivalent to the random effect in terms of statistical testing and point estimates of coefficients of fixed effects, however, the variance covariance matrix of random effects will not be estimated. The mean treatment difference ($\mu_{C1 \text{ INH}} - \mu_{placebo}$) will be estimated with a 95% CI provided. The upper confidence bound of 95% CI must be less than 0 in order for C1 INH to be considered superior to the placebo.

A summary of NNA during each treatment period by treatment sequences will be provided for the Full Analysis Set.

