10.2 Key Secondary Efficacy Variable(s) and Analysis

The key secondary efficacy variables are listed as following:

- 1. The proportion of subjects meeting the criterion of at least a 50%, 70%, 90% and 100% reduction in the NNA during the 2000 IU C1 esterase inhibitor [human] liquid for injection treatment period relative to the placebo period.
- 2. The NNA excluding the first 2 weeks of each treatment period.
- 3. The proportion of subjects meeting the criterion of at least a 50%, 70%, 90% and 100% reduction in the NNA for the 2000 IU C1 esterase inhibitor [human] liquid for injection treatment period relative to the placebo period excluding the first 2 weeks of each treatment period.

Key secondary efficacy endpoints 1 and 3 are defined as achieving a \geq 50% reduction in the NNA (P_R) during the 2000 IU C1 esterase inhibitor [human] liquid for injection treatment period relative to the placebo period.

The Key secondary endpoints 1 and 3 will be analyzed as the proportion of subjects meeting the above clinical response criterion (P_R). The analysis will be conducted over the Full Analysis Set from the first two treatment sequences. The null hypothesis is that P_R is less than or equal to 0.2, and the alternative hypothesis is that P_R is greater than 0.2 as below:

$$H_{0:} P_{R} \leq 0.2$$
vs
$$H_{1:} P_{R} > 0.2$$

The proportion P_R will be estimated with an exact 95% CI. The lower limit of the 95% CI for the proportion will be compared with 0.2. This is equivalent to testing the null hypothesis against the alternative hypothesis at a 1-sided alpha level of 0.05 using the binomial distribution.

Analysis of key secondary endpoint 2 will follow the same methods (ie, the linear mixed effect model) used for the primary efficacy endpoint.

The key secondary analyses will be performed using the Full Analysis Set and the Per-protocol Set.

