- The primary efficacy endpoint will be compared for the active treatment to the placebo in the Full Analysis Set, including subjects in the A/A treatment sequence. In this analysis, the same method used in the analysis for the primary efficacy endpoint will be applied.
- The primary efficacy analysis will be repeated with exclusion of data after any major protocol deviation.

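### SAP 19.4 item 21 drops a subject from the Per-protocol Set for one missing attack form, so exclusion becomes likelier as attacks, the outcome, accumulate

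*SAP*

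**What the plan says.** SAP Section 4.6 defines the Per-protocol Set partly through an appendix: "Refer to Appendix 19.4 for the protocol deviations that exclude subjects from the Per-protocol Set". That appendix, Section 19.4, states the consequence: "Subjects who satisfy these protocol deviations will be excluded from the Per-protocol Set". Item 21 on its list is "Investigator did not complete a separate angioedema attack CRF for each attack", the form being the one that follows the investigator's review of the electronic diary. It gives no number or share of forms, and no time limit for correction. Other items on the list do set a quantity: compliance below 85% (item 18), three or more consecutive missed doses (item 19), three or more consecutive doses of the wrong treatment (item 27).

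Protocol Section 7.2.2.2 creates one form per attack: "The investigator will complete a separate angioedema attack CRF for each attack based upon their review of the data in the subject diary". The endpoint is built on the same count. SAP Section 10.1: "The NNA is expressed as the number of attacks per month (ie, 30.4 days) of exposure".

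On where the list is used, SAP Section 10.2 says "The key secondary analyses will be performed using the Full Analysis Set and the Per-protocol Set". Section 10.4 repeats the clinical response summary on the Per-protocol Set. Section 10.5.1 adds "The primary efficacy analysis will be repeated with exclusion of data after any major protocol deviation", and Section 19.4 is the SAP's itemised list of major deviations. The primary analysis itself uses the Full Analysis Set in sequences A/B and B/A (Section 10.1), and Section 10.3 rests study success on that analysis alone.

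**The concern.** A Per-protocol Set should be defined by features that do not depend on the outcome, such as eligibility, treatment received and compliance. Item 21 is different. A subject with no attacks cannot meet it, and each further attack is another chance to meet it. Subjects with the most attacks are thus the likeliest to leave, for a lapse by the site that says nothing about the treatment they received.

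At stake is the use of the supportive analyses. If the Per-protocol and Full Analysis Set results for the key secondaries differ, part of the difference may come from selection on attack count rather than from protocol adherence. If they agree, the agreement is less informative than it looks. The sensitivity analysis in Section 10.5.1 has a related problem, because a data cut triggered by item 21 is more likely in a period with more attacks.

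**Working it through.** **The plan's own figure.** The SAP gives no figure for item 21: no form-miss rate and no expected Per-protocol size. The nearest stated figure is the primary power in Section 2.5: 44 subjects, difference 1.0 attack per month, SD of the difference 2.0, one-sided 0.025. SE = 2.0/√44 = 0.302. A noncentral t with 43 df gives power 0.900 and the normal approximation gives 0.913. The stated 90% is reproduced, and the difference of 1.0 sets the scale below.

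**Exclusion by attack count.** Let q be the chance that any one attack ends without its own form. It is assumed constant and independent across attacks. For n attacks over both periods, P(excluded) = 1 − (1 − q)^n.

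| q (assumed) | n = 0 | n = 5 | n = 10 | n = 20 |
|---|---|---|---|---|
| 1% | 0% | 4.9% | 9.6% | 18.2% |
| 2% | 0% | 9.6% | 18.3% | 33.2% |
| 5% | 0% | 22.6% | 40.1% | 64.2% |

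The rise with n holds for any constant q above 0. Only its steepness depends on q.

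**At the design rates.** A period is 98/30.4 = 3.22 months. Take 2.0 attacks per month on placebo (the entry minimum, used as an illustration) and 1.0 on active (2.0 less the design difference of 1.0). That gives 6.45 + 3.22 = 9.67 attacks per crossover subject. Item 21 alone then excludes:

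- q = 1%: 9.3%, leaving about 47 of the 52 crossover subjects
- q = 2%: 17.7%, leaving about 43
- q = 5%: 39.1%, leaving about 32

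The chance of at least one trigger in the placebo period against the active period is 6.3% v 3.2%, 12.2% v 6.3% and 28.2% v 15.2% respectively.

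**Effect on Per-protocol estimates.** This was simulated with 400,000 subjects and gamma-Poisson counts at the same mean rates. The between-subject CV was 0.5 or 0.8, and the treatment ratio varied between subjects with log-SD 0.5. All of these are assumptions. The Full Analysis Set difference is −1.0.

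| q | Per-protocol difference, CV 0.5 | CV 0.8 |
|---|---|---|
| 1% | −0.97 | −0.95 |
| 2% | −0.95 | −0.90 |
| 5% | −0.89 | −0.77 |
| 10% | −0.78 | −0.60 |

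The proportion with at least a 50% reduction moves by at most about 2 points (for example 0.589 to 0.596 at q = 2%, CV 0.5). Counts cover whole periods, so these results only approximate the key secondaries that omit the first two weeks.

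**The case against.** The strongest reply concerns weight.

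**No confirmatory decision depends on this.** This stands. A reader might infer that item 21 undermines the primary result, or that the Per-protocol Set is the check on it. The text available shows that set used only for the key secondaries, beside the Full Analysis Set, and for a responder summary. The opening of SAP Section 10.5.1 could not be consulted, so a Per-protocol repeat of the primary analysis can be neither confirmed nor ruled out.

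**The likely distortion is modest.** This also stands at low q. A reader might infer that the rule flatters the drug. The simulation shows the opposite for the mean difference, because both periods of a high-attack subject leave together and the absolute difference shrinks. Material change needs q of about 5–10%.

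**Lapses may cluster by site, and cleaning may catch most of them.** Protocol Sections 9.1 and 9.2 provide for source verification, checks for omissions and site queries. Clustering would weaken the link with attack count, and cleaning would lower q. But item 21 does not say that it covers only forms still missing after cleaning, and a subject without attacks remains immune.

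**The form is more than paperwork.** It records the investigator's review, and Protocol Section 7.2.2.1 excludes some swelling, such as that due to trauma or arthritis. This stands, and it limits the remedy: raw diary entries should not be counted unreviewed.

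**The Section 10.5.1 cut.** A reader might infer that the cut falls immediately after an attack and so inflates the rate up to that point. The SAP does not say whether an item 21 deviation is dated to the attack, to the missed entry or to its discovery at monitoring, so the direction of bias cannot be stated.

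**Conclusion.** The concern holds for the supportive analyses. Followed as written, item 21 makes membership of the Per-protocol Set depend on the attack count, and with it the Per-protocol key secondary analyses and the responder summary. Through the same list it also reaches the sensitivity analysis that drops data after a major deviation, with a direction that the SAP leaves open. The primary Full Analysis Set test and the success rule are not affected.

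The size rests on q, which is assumed, and on independence across attacks. At q of 1–2% a subject with 10 attacks is excluded with probability 10–18%, but the simulated Per-protocol difference moves only from −1.0 to between −0.97 and −0.90. At 5% the exclusion becomes large enough to cloud interpretation. The change is worth making because it is cheap and the rule does nothing useful that a query would not do better.

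**What to change.** Take item 21 off the Per-protocol exclusion list in SAP Section 19.4, and state that it does not trigger the data cut in Section 10.5.1. Before unblinding, resolve every diary-reported attack that lacks a form by site query and investigator review of the diary entry against the attack definition in Protocol Section 7.2.2.1. Count the attacks so confirmed, and continue to report the lapse as a deviation under SAP Section 6.

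The cost is one list item removed and a sentence or two added. The query process already exists, and the primary analysis does not change. The downside is that a few subjects with a late or unresolved form stay in the Per-protocol Set.

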2. STUDY DESIGN

2.1 General Study Design

This is a phase 3, randomized, double-blind, placebo-controlled, two-period, three-sequence, partial crossover study to evaluate the efficacy and safety of subcutaneous (SC) administration of 2000 IU of C1 esterase inhibitor [human] liquid for injection for the prevention of angioedema attacks in adolescents and adults with hereditary angioedema (HAE).

Individual participation from the screening visit through the 1-month post-treatment visit will be approximately 9 months (up to 21-day screening period, two 14-week treatment periods [total 28 weeks] with no washout between treatment periods, and 1-week and 1-month post-treatment follow-up visits). A study flow chart is shown below (Figure 1).

Participants are expected to receive blinded investigational product (C1 esterase inhibitor [human] liquid for injection or placebo) twice weekly (every 3 or 4 days) for 14 weeks in each treatment period. Eligible subjects will be randomized to one of the three treatment sequences, A/B, B/A, or A/A (Table 1).

Table 1:Treatment Sequences

Sequence	Treatment: Period 1/Period 2	Approximate Number of Subjects Randomized
1	A/B	26
2	B/A	26
3	A/A	14

Treatment A=2000 IU (4.0 mL) C1 esterase inhibitor [human] liquid for injection administered SC twice weekly (every 3 or 4 days) for 14 weeks.

Treatment B=Placebo (4.0 mL) administered SC twice weekly (every 3 or 4 days) for 14 weeks.

Figure 1: Study Design Flow Chart

Subject Participation ≈9 months

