8. EXTENT OF EXPOSURE AND TREATMENT COMPLIANCE

8.1 Exposure to Investigational Product

For all treated subjects, including the ones who had early termination, treatment exposure is the duration between the first dose date and last dose date in each treatment period. Average daily dose, total dose, total number of doses, total exposure, length of exposure to investigational product (<=1 wk, >1 - <=2 wk, >2 - <=5 wks, >5 - <=10 wks, >10 - <=14 wks, >14 - <=18 wks, >18 - <=24 wks, >24 - <=28 wks, >28 wks), and treatment compliance will be summarized by treatment for the Safety Set and Full Analysis Set.

A listing will be created by subject and treatment and will show the date and time of dose administration for each treatment given for the Safety Set.

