10.5.2 Multiple Imputation Analysis

Analysis based on imputing missing values by drop out reason (Protocol Section 4.4.1) are added as sensitivity analysis to the primary efficacy analysis. The primary imputation method within the sensitivity analysis will be the multiple imputation method for the Full Analysis Set described below in this section.

A subject is considered to have missing values in case he/she leaves the study prematurely. The fraction of non-missing data (f) and normalized number of HAE attacks (NNA_{observed}) will be determined per treatment period and subject as follows:

17 Aug	2017
--------	------

Category	Level of Participation per Treatment Period	Fraction of non-missing data (f) per Treatment Period	Observed normalized number of HAE attacks (NNA _{observed})
А	Subject is not discontinued from the study	1	As outlined in Section 8.1
В	Subject is discontinued from the study in a treatment period	Days of participation / scheduled length of treatment period (days)	As outlined in Section 8.1
С	Treatment period 2 among subjects who discontinued during treatment period 1	0	

Days of participation will be calculated as defined in Section 8.1 and scheduled length of treatment period is the intended length, i.e., 14 weeks for analysis equals $14 \times 7=98$ days.

The missing data will be imputed with NNA according to the sensitivity analysis by drop out reason. The normalized number of HAE attacks to be used for the sensitivity analysis (NNA_{analyzed}) will be calculated based on the observed number (NNA_{observed}) and the imputed number (NNA_{imputed}) taking into account the fraction of non-missing data (f) as:

 $NNA_{analyzed} = f \times NNA_{observed} + (1 - f) \times NNA_{imputed.}$ (Equation 10.1)

Values for NNA_{observed} will be determined as outlined in the above table; values for NNA_{imputed} will be determined for each subject and period with missing data depending on the sensitivity analysis as described below.

If a subject discontinues prematurely in treatment period 1, his/her NNA_{analyzed} value during treatment period 2 will be imputed by the median of the non-missing NNA_{observed} from all subjects who have complete data within the same treatment as that the subject is expected to take in treatment period 2.

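### SAP 19.4 item 22 removes a subject from the Per-protocol Set for C1 INH prophylaxis begun after the attack-counting window has closed

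*SAP*

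**What the plan says.** SAP 4.6 defines the Per-protocol Set as Full Analysis Set subjects who "complete scheduled primary assessments for 6 study weeks and who do not have pre-defined protocol deviations that may affect the primary efficacy endpoint". SAP 19.4 opens its list in the same terms: "The following protocol deviations are classified as major protocol deviations that may affect the primary efficacy endpoint". Any subject who meets an item leaves the set entirely.

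Item 22 covers concomitant C1 INH other than study drug, used "for prophylaxis against angioedema attacks after randomization upto 1 wk FU period". Item 23 covers an overlapping group of therapies but closes earlier: "Initiation of long term therapy (including IV C1-INH, Transexamic acid or androgen therapy) after randomization upto the last dose".

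NNA counts attacks during a treatment period (SAP 10.1). For early stoppers, "If a subject discontinues during the treatment period, the denominator of the NNA will be the days on treatment for that subject". SAP 10.1 gives no calendar end date for completers. Two other sections suggest one. In SAP 8.1, "treatment exposure is the duration between the first dose date and last dose date in each treatment period". In SAP 10.5.2, "scheduled length of treatment period is the intended length, i.e., 14 weeks for analysis equals" 98 days.

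Protocol 7.1.5 places the 1-week visit at 1 week ± 1 day after the last dose. Protocol 5.2.2 prohibits C1 INH prophylaxis until the 1-month post-treatment visit.

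**The concern.** Once the NNA window has closed, the attack count is fixed, and prophylaxis started afterwards cannot alter it. Such use therefore fails the criterion that SAP 4.6 and 19.4 set for exclusion, yet item 22 deletes the subject's data from both periods. Its cut-off matches neither the NNA window, nor item 23, nor the protocol's prohibition.

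The word 'concomitant' does not confine item 22 to time on treatment, because SAP 9 counts medications started up to the 1-month visit as concomitant.

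The situation can plausibly arise. Adults on C1 INH prophylaxis are eligible and form a randomization stratum. Protocol 5.2.1 allows such a subject to be discontinued for marked deterioration after at least 3 weeks of study drug, and asks the investigator to arrange treatment in line with past HAE therapy. Take an A/B subject who completes active treatment, deteriorates on placebo, stops, and resumes C1 INH within a week. That subject has NNA in both periods and can meet the 6-week requirement, but item 22 removes both values. Exclusion of this kind may be related to outcome.

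What is at stake is the supportive evidence. In the SAP text available, the Per-protocol Set is used for the key secondary analyses (SAP 10.2) and the clinical-response summary (SAP 10.4).

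**Working it through.** **Plan's own figures.** 14 weeks × 7 = 98 days, as in SAP 10.5.2. Dosing is "twice weekly (every 3 or 4 days) for 14 weeks in each treatment period", so 14 × 2 = 28 doses, matching the 28 doses per period in protocol 4.4.4.

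**Day of dose 28.** There are 27 gaps after day 1, alternating between 3 and 4 days.

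- First gap 3 days: 1 + 14×3 + 13×4 = day 95.
- First gap 4 days: 1 + 13×3 + 14×4 = day 96.

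**Days covered by item 22 after the last dose.** The visit is at 7 ± 1, that is 6 to 8 days after the last dose, counting the visit day.

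| NNA window ends at | Post-dose days inside | Post-dose days outside |
|---|---|---|
| Day 98, dose 28 on day 95 | 98 − 95 = 3 | 3, 4 or 5 |
| Day 98, dose 28 on day 96 | 98 − 96 = 2 | 4, 5 or 6 |
| Last dose (SAP 8.1) | 0 | 6, 7 or 8 |

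The minimum is 6 − 3 = 3 and the maximum on the 98-day reading is 8 − 2 = 6. For a discontinuer the denominator is days on treatment, so the whole follow-up week is outside.

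**Effect on key secondary 2 (NNA without the first 2 weeks of each period).** Inputs from SAP 2.5 are n = 44 and SD of the difference 2.0. The SD is stated for NNA and assumed to hold here. The documents do not give the number of subjects item 22 would remove on post-window days; 1 to 4 is an assumed range. SE = SD/√n.

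- 44 subjects: 2/√44 = 0.302
- 43 subjects: 2/√43 = 0.305 (+1.2%)
- 40 subjects: 2/√40 = 0.316 (+4.9%)

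**Effect on key secondaries 1 and 3 (responder proportion tested against 0.2).** The starting point is 19/44, the count nearest the design value of 0.44. Limits are exact (Clopper-Pearson) lower 95% limits.

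| Case | Proportion | Lower limit |
|---|---|---|
| None removed, 19/44 | 43.2% | 28.4% |
| 1 responder removed, 18/43 | 41.9% | 27.0% |
| 4 responders removed, 15/40 | 37.5% | 22.7% |
| 1 non-responder removed, 19/43 | 44.2% | 29.1% |
| 4 non-responders removed, 19/40 | 47.5% | 31.5% |

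The lower limit stays above 20% in every case.

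**The case against.** Six points can be made for the plan.

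1. *The wording is ambiguous.* Up to the follow-up period could mean until that period begins, which would leave no excess. This is possible but strained: item 23, the next entry, names the last dose when that is what is meant.

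2. *The cut-off has a visible origin.* SAP Table 4 schedules concomitant medications, attack monitoring and AAS at the 1-week visit and not at 1 month. That may explain where item 22 stops. It does not let later use change a closed attack count. Protocol Table 3 now extends medication and attack recording to 1 month.

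3. *The use is prohibited anyway.* True: under protocol 5.2.2 it is a genuine deviation and should be reported as one. The SAP's test for exclusion is different, namely whether the deviation may affect the primary endpoint.

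4. *Other items are loose too.* Items 11, 13 and 14 (thrombotic history, allergy, pregnancy or breastfeeding) have no obvious direct effect on attack counts, and item 24 has no end date. This is fair, but it does not justify item 22.

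5. *Three days is not an absolute minimum.* This stands. The figure assumes alternating 3- and 4-day gaps and counts the visit day. Leaving out the visit day gives 2. With dose 28 as early as days 92 to 94 and a visit at +6, the count on the 98-day reading is 0 to 2. The discontinuer case does not depend on this count.

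6. *Few subjects can be affected.* Also true. The subject must be in sequence A/B or B/A, meet the 6-week rule, have no other exclusion, and first use C1 INH prophylaxis within about a week of the last dose. For key secondaries 1 and 3 the subject must also have NNA in both periods, so Period 1 dropouts lose nothing there.

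**Conclusion.** The concern holds and is minor. Item 22 excludes subjects for conduct that cannot affect the endpoint the list is meant to protect. On the nominal schedule the excess is 3 to 6 days with a 98-day period, or 6 to 8 days if the period ends at the last dose; for discontinuers it is the whole follow-up week.

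The consequence is confined to supportive Per-protocol results. The primary analysis uses the Full Analysis Set, SAP 10.3 rests study success on the primary analysis alone, and the key secondary analyses on the Full Analysis Set do not change. The number of subjects affected and the direction of any bias cannot be established from the documents. The assumed removal of 1 to 4 subjects shows only that the effect would be small.

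**What to change.** Before unblinding, reword the end of item 22 so that it closes at the last dose of investigational product, as item 23 does, or at the end of the NNA observation window if that is later. C1 INH prophylaxis inside that window stays an exclusion. List later use, up to the 1-month visit, as a protocol deviation under protocol 5.2.2 that does not remove the subject from the Per-protocol Set.

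The cost is one phrase in SAP 19.4, with no protocol amendment and no new data. If the NNA-window option is chosen, the SAP must also state the calendar end of the treatment period for completers, which SAP 10.1 leaves open.
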